### **Methods: Monitoring**

Data monitoring 20a Administrative data will be collected retrospectively using de-identified datasets with permissions from AHS. Patient data will be self-entered electronically, without study team involvement. The same study coordinator will be assisting with clinical implementation at all sites for consistency. Because the intervention in this trial is the implementation of a clinical pathway a data monitoring committee will not be required.

Harms 21 Monthly teleconferences will alert study staff to any concerns. Patient adverse events are not a risk with this trial. If the implementation of the CP leads to significantly longer recovery based on the primary outcome at any of the sites, the study protocol will be stopped.

Auditing 22 The investigator will be in contact with the study coordinator consistently throughout the trial and monthly teleconferences will be a form of qualitative audit with each site.

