The CP has grown out of the work of the MNCY SCN workgroup on pediatric concussion. It includes several elements, including diagnostic and prognostic tools, discharge instruction forms, information leaflets, and access to an informational website and for patients and parents. To develop the CP, the workgroup reviewed the existing CPGs for concussion diagnosis and management, and generated a "clinical knowledge topic" document that provides AHS practitioners with information and guidance about concussion care, including care pathways and algorithms. The CP originally incorporated tools such as the Acute Concussion Evaluation (ACE) for identification and diagnosis, the PECARN rule for determining the need for CT scan, and the 5P rule for predicting risk of persistent symptoms. The CP also was intended to include a parent/patient handout developed by the workgroup and approved by AHS. The CP for the study will be based on the most up-to-date evidence and consensus guidelines, as reviewed by the MNCY SCN pediatric concussion workgroup. Although the CP is not expected to change during the study period, it certainly could evolve over time as the evidence base for concussion increases, and consensus guidelines are updated. The goal is to reduce practice variation and improve care by using a CP to align acute diagnosis and management with evidence-based CPGs.

Qualitative interviews and site visits led to iterative changes in the CP to account for practice variations between sites and to enhance clinician buy-in. Initially the ACE tool was chosen as the primary CP tool for physician assessment; however, physicians felt that the ACE overlapped too much with existing assessments and did not direct patient care. Based on this feedback, the 5P rule scoring rubric was chosen instead of the ACE. The 5P risk score was implemented to enable automatic referrals of children at high risk of persistent postconcussive symptoms to a specialty concussion clinic, and also to encourage referral of low and medium risk children for follow-up by primary care providers.

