Secondary outcomes also will include measures of physician adherence, the number of unique website hits per IP address, the proportion of patient- and parent-reported adherence to physician discharge recommendations, the proportion of diagnosed concussions per visit (predicted to increase as physicians identify and code the injuries correctly), and the proportion of CT scans ordered per diagnosed concussion (predicted to decrease because the CP will include prediction rules for CT scanning in concussion).

12c *Table 3: Process and clinical outcomes*

| Outcome measure      | Description         | Details  |
|-----------------------------|----------------------------|---|
| Primary clinical outcome    | Time to symptom resolution | Weekly ratings by patients and parents of whether patient has returned to pre-injury status   |
| Secondary clinical outcomes | Postconcussive symptoms    | Weekly ratings on Health and Behaviour Inventory  |
|                             | Quality of life            | Weekly ratings on PedsQL  |
|                             | Satisfaction with care     | Post-visit rating of overall satisfaction with acute care   |
| Primary process outcome     | Physician adherence        | Proportion of completed discharge forms per diagnosed concussion    |
| Secondary process outcomes  | Patient/parent adherence   | Proportion of patient and parent reports of adherence to physician discharge recommendations involving rest, return to school, and return to play |
|                             | Patient/parent adherence   | Number of unique website hits per IP address  |
|                             | Physician adherence        | Proportion of diagnosed concussions per visit   |
|                             | Physician adherence        | Proportion of CT scans ordered per diagnosed concussion   |

Qualitative interviews and site surveys resulted in the discharge form being replaced by the 5P risk score sticker. To assess adherence, the study team recorded the number of 5P assessments completed by each site over the course of data collection.

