12d *Health care utilization.* We will assess the impact of the implementation of the CP on health care utilization using data from the National Ambulatory Care Reporting System (NACRS). Relevant outcomes will include acute care length of stay and return visits within 72 hours following acute care discharge. Appropriate procedures will be used to link administrative and health data. Use of NACRS data allows efficient capture of return visits, regardless of whether the patient returns to the index site. We will also use administrative data from AHS to assess health care utilization for pediatric patients with concussion. For each concussion diagnosed at the target sites, we will track the duration of stay in the ED, number of subsequent outpatient visits, and number of referrals to other health care services.

*Healthcare costs.* Payer costs associated with acute care for pediatric patients with concussion will be accounted for, based on ED visits, return visits, and physician fees, as well as subsequent outpatient care, which will be determined from the AHS administrative database. Costs for ED visits will be based on standard methodologies using resource intensity weightings (RIWs). Physician fees associated with ED and outpatient visits, including those for laboratory and diagnostic imaging services, will be captured through associated AHS billings. Cost data will be presented in Canadian dollars for the standard price year of 2014.

Participant timeline 13a *Project phases.* As shown in the Project Timeline below, the project will be divided into four phases. During the pre-implementation phase, which will last 12 months, we will complete site visits and key informant interviews, develop the intervention strategy, seek site approvals for the planned intervention, conduct a launch meeting, and complete randomization. The implementation phase will take place over the next 10 months. According to the stepped wedge design, data collection will occur continuously from 2 months prior to implementation at any site until 2 months after the CP is implemented at all four sites. Data collection will include the monitoring of outcomes, which are described below, during the course of the stepped wedge trial, which will last about 10 months.

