17b The web portal will send email reminders to participating families to complete serial symptom inventories. No contact will be made by the study team unless families reach out voluntarily. Ideally, symptom data will be collected until participants fully recover, however, participants can stop entering data, or leave the study at any time.

Data management 18 The study team will not directly access AHS databases or systems. Administrative data will be accessed externally by an AHS MyChild analyst. The variables collected will be obtained for all children diagnosed with concussion at any of the participating AHS facilities during the conduct of the stepped wedge clinical trial. The data will be de-identified, except for children whose parents have consented to linkage of web portal responses with health records. Individual data entered through the web portal by parents and children will download into the secure REDCap database. The database servers will be located under Canadian jurisdiction and be administered by the Clinical Research Unit of the University of Calgary. These servers are part of the CRU infrastructure and maintained in accordance with strict security and privacy controls.

Results from the project will be reported in aggregate format. If individual materials are presented, all personal identifiers will be removed. These safeguards should maintain confidentiality and minimize any risks associated with participation in the project.

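### Item 21 rules out patient adverse events without qualification, although CT per diagnosed concussion is predicted to fall and no specified outcome identifies an intracranial injury found after the index visit

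*Protocol*

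**What the plan says.** Item 21 (Harms) states: "Patient adverse events are not a risk with this trial". No reason or qualifier is given. The following sentence says that if the pathway "leads to significantly longer recovery based on the primary outcome at any of the sites, the study protocol will be stopped".

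Item 12b lists CT scans ordered per diagnosed concussion as a secondary outcome, "predicted to decrease because the CP will include prediction rules for CT scanning in concussion". Table 3 (item 12c) files it under physician adherence. The description of the pathway in the Introduction names "the PECARN rule for determining the need for CT scan" among the tools it originally contained.

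Item 12d covers what happens after the index visit: "Relevant outcomes will include acute care length of stay and return visits within 72 hours following acute care discharge". NACRS is chosen because it finds returns "regardless of whether the patient returns to the index site". Later outpatient visits and referrals are also tracked, and physician fees, "including those for laboratory and diagnostic imaging services, will be captured through associated AHS billings". Under item 18 the administrative variables are "obtained for all children diagnosed with concussion at any of the participating AHS facilities", not only for portal users.

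**The concern.** The trial tests a pathway that is expected to alter an imaging decision in children with head injury. When imaging changes, a delayed diagnosis of intracranial injury is a foreseeable possibility, however small. A protocol that declares the risk absent gives no reason to look for it.

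What is at stake is interpretation. A fall in the CT ratio would be reported as a predicted success on adherence. Nothing specified beside it would separate a 72-hour return for headache from a return at which an intracranial injury was found. The reader of the trial report could not tell whether delayed diagnoses were absent or simply not sought.

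**Working it through.** **1. Is the sentence consistent with the rest of the protocol?** Item 21 denies any adverse-event risk, then provides for stopping if recovery is significantly longer. Item 12b attributes a predicted fall in CT per diagnosed concussion to CT rules in the pathway. Both treat an effect on patients or their diagnostic work-up as possible, so the unqualified denial has no support.

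**2. Does any specified outcome identify a later intracranial diagnosis?**

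| Outcome (items 12a to 12d) | Identifies it? |
|---|---|
| Time to symptom resolution, HBI, PedsQL, satisfaction | No; self-report through a voluntary portal |
| Discharge forms or 5P assessments, patient/parent adherence, website hits | No |
| Concussion diagnoses per visit, CT per concussion | No; concern the index visit |
| Length of stay, 72-hour returns, outpatient visits, referrals | Not as specified; no diagnosis attached |
| Costs, including imaging fees | Shows that a scan took place, not what it found |

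The nearest measure is the 72-hour return, which is already captured at any site.

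**3. How precise would a count be?** The protocol gives no figure on this point to reproduce. Inputs:
- Diagnoses in 12 months (item 9): 2,098 coded S06.0 (concussion) and 1,517 coded S09.9 (head injury, unspecified).
- Trial length (item 13a): about 10 months, with two-month steps, so the four sites spend 2, 4, 6 and 8 months before the pathway and 8, 6, 4 and 2 after it.
- ED volumes (item 9), as a proxy for concussion volume: Calgary 77,000 + 15,000 = 92,000; Stollery 50,000; the other two Edmonton sites 18,000 together, taken here as 9,000 each (assumption). Total 160,000.

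The share of children seen before the pathway depends on the randomised order:
- Largest site first: (92×2 + 50×4 + 9×6 + 9×8) / (160×10) = 510/1,600 = 31.9%.
- Largest site last: (92×8 + 50×6 + 9×4 + 9×2) / 1,600 = 1,090/1,600 = 68.1%.

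Children over 10 months: S06.0, 2,098 × 10/12 = 1,748; S06.0 plus S09.9, 3,615 × 10/12 = 3,012.5.

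Exact (Clopper-Pearson) upper 95% limit with zero events: 1 − 0.025^(1/n).

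| Group | Share in phase | n | Upper limit at 0 events |
|---|---|---|---|
| S06.0 | 31.9% | 557 | 0.66% |
| S06.0 | 50% (equal site volumes) | 874 | 0.42% |
| S06.0 | 68.1% | 1,191 | 0.31% |
| S06.0 + S09.9 | 31.9% | 960 | 0.38% |
| S06.0 + S09.9 | 50% (equal site volumes) | 1,506 | 0.24% |
| S06.0 + S09.9 | 68.1% | 2,052 | 0.18% |

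**4. How many events?** The documents give no rate, so the following rates are assumptions. For n = 874, the expected count is n×r and the chance of none is (1 − r)^n: r = 0.02% gives 0.2 events and 84%; r = 0.1% gives 0.9 and 42%; r = 0.5% gives 4.4 and 1%. Zero to a few events is the realistic range. The count would bound the rate in each phase; it could not test a difference.

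**The case against.** The strongest reply has five parts.

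- *The CT premise is soft.* The prediction concerns a ratio, and item 12b also predicts that its denominator, diagnosed concussions per visit, will rise. Part of the fall could occur with no child's imaging changed. The Introduction lists the CT rule only among tools originally incorporated, and Table 2 names no CT tool. This stands as a limit, although item 12b still attributes the fall to the CT rules.
- *Much is already planned.* Any-site returns, outpatient visits, referrals, imaging billings, twice-monthly champion feedback and monthly teleconferences all exist. True, but the administrative measures are utilization or cost counts, and the feedback channels depend on a site hearing of a child who may have returned elsewhere.
- *Silence is not inability.* A reader might infer that the planned data cannot show a delayed diagnosis. The documents do not support that: the lists in items 12d and 30a are not said to be complete, and index cases are found by ICD code, so return-visit codes may be retrievable. Only the claim that this is not specified holds.
- *Splitting an outcome by diagnosis is analysis-plan detail.* This has some force, and it is one reason for the low severity. The unqualified sentence in item 21, however, is the protocol's own.
- *The denominator moves.* If coding shifts with the pathway, S06.0 children before and after may differ in case mix. This stands, and it determines the choice of denominator in the fix.

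A further tempting reading is that the pathway endangers children. Nothing in the documents shows this; a sound rule may remove only scans that were not needed.

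**Conclusion.** The point holds at low severity, as a cheap improvement. The sentence in item 21 is unsupported, and no specified outcome distinguishes a return with a delayed intracranial diagnosis from any other return. Harm is not shown to be likely. Neither can the risk be called rare on the evidence here, because no rate is given.

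The precision figures rest on the 10-month duration, the 2015-2016 diagnosis counts, ED visits as a proxy for concussion volume, an even split between the two smaller Edmonton sites, and independence of children within the four sites.

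**What to change.** **Item 21.** Replace the sentence with: *Delayed diagnosis of intracranial injury is a possible risk and will be counted as described in 12d.*

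**Item 12d.** Split the planned 72-hour NACRS returns by return-visit diagnosis. Report descriptively, by pathway status, the number and proportion of index children who return with an intracranial-injury diagnosis other than concussion. Give an exact confidence interval and place it beside the CT result. Set no test and no threshold. Use S06.0 plus S09.9 as the main denominator, because coding is predicted to shift between these categories, and show S06.0 alone second. Item 10 already brings S09.9 cases into a sensitivity analysis.

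**Cost.** One sentence and one field on returns already to be drawn; no patient procedures. The AHS analyst must first confirm the field, since the data elements listed in item 30a do not name it.

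**Downsides.** Zero to a few events are likely. Injuries found after 72 hours are missed. The interval ignores clustering by site and any case-mix shift that remains after S09.9 is added. A zero count would exclude only rates above roughly 0.2% to 0.4% on the main denominator.

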## Ethics and dissemination

|                          |     |  |
|--------------------------|-----|--|
| Research ethics approval | 23  | Approval will be obtained by the Conjoint Health Research Ethics Board at the University of Calgary.   |
| Protocol amendments      | 24  | Amendments will be submitted to the research ethics board.   |
| Consent or assent        | 25a | Consent will be obtained from sites through signed agreements. Participant consent will be passively collected when families voluntarily access the web portal and provide electronic consent.   |
| Confidentiality          | 26  | Confidentiality will be maintained by assigning all participants who use the web portal with an identification number. All data collected during the study will use that number for identification purposes. Computer databases will use the identification number for designation purposes, and will not contain participant names. Results from the project will be reported in aggregate format. If individual materials are presented, all personal identifiers will be removed. These safeguards should maintain confidentiality and minimize any risks associated with participation in the project.   |
| Declaration of interests | 27  | There are no declarations of interest to disclose on behalf of the investigators.  |
| Access to data           | 28  | The final dataset will only be accessible to the study team and will not include patient identifiers.  |
| Dissemination policy     | 30a | The proposed evaluation of the CP for acute care of pediatric concussion will be an important step in improving the outcomes of children with concussion. We expect that the study will yield critical knowledge regarding the success of CP implementation at multiple levels: uptake of and adherence to the CP among front-line staff, as well as adherence by patients and parents; effects on clinical outcomes, including patient satisfaction and health outcomes; and impact on health care utilization and costs. Standardizing care via the successful implementation of the CP should result in significant benefits to patients, while reducing the burden on the health care system posed by concussion. In summary, the project will advance knowledge about CP implementation and outcomes; build capacity by involving students and early career investigators; inform clinical decision-making by assisting health care providers involved in the acute care of pediatric concussion; improve the health of children with concussion; and reduce the public health and socioeconomic burdens of concussion. |

The MNCY SCN pediatric concussion workgroup is working closely with the AHS Clinical Knowledge & Content Management (CKCM) group in the development of its clinical guidelines and CPs. CKCM is a key component of the AHS Provincial Clinical Information System (CIS) initiative, which will support a single integrated electronic health system. The CKCM group is assisting in the development of physician order sets, clinical documentation, and other tools that will facilitate implementation of the CP. With CKCM's leadership, the CP will be placed in a provincial repository to be used and adopted by the provincial CIS, as well as the existing legacy electronic systems until a provincial CIS is fully implemented. This will simplify access to a single provincial clinical standard for concussion. Further, as the provincial CIS design and build begins in late 2017, concussion will be included in the system design, facilitating implementation by inclusion in the electronic CIS. CKCM can also assist in the identification of data elements and measures, and facilitate study linkage to the AHS provincial data warehouse for data reporting and analytics. The AHS Analytics program draws data from a number of information systems, and reports this data to national databases such as NACRS (national ambulatory care reporting system). The available data elements are available on the AHS website, including demographics information, symptom/presenting complaint, arrival/admission and discharge date from ED, and consult information.

30b We anticipate three major project deliverables:

(1) A summary report that includes several key components: study rationale; study design; findings from site visits and key informant interviews; planned intervention strategies; results of the CP implementation; and a plan for dissemination.

(2) A website that facilitates patient and parent engagement in CP implementation by providing them with evidence-based information about concussion recovery and management, along with tools to track recovery across time.

(3) Widespread scientific and professional dissemination through presentations to pediatric acute care providers in multiple settings and at professional and scientific conferences, as well as through peer-reviewed publications in clinical and scientific journals.

30c Knowledge sharing and translation is an integral part of our project, which by definition involves the translation of evidence-based guidelines into clinical practice. We will seek ongoing input from multiple stakeholders during all phases of the study. During the pre-implementation phase, when co-constructing the intervention strategy for implementing the CP, we will draw on the collective expertise of the study team, many of whom are acute care clinicians, as well as on input from physicians, nurses, and administrators at each of the participating sites. During the implementation phase, we will remain in frequent communication with the site champions, to obtain their feedback, troubleshoot local issues, and promote sustainability.

We will involve patients and their parents in the project by inviting study participants to provide feedback on the care they receive and to report on patient-centered outcomes. We have invited two persons with a history of concussion to collaborate on the project by providing ongoing feedback on the CP and its implementation. Throughout the project, we plan to engage a variety of community partners (e.g., Parachute, Brain Injury Canada, Public Health Association of Canada), research networks (e.g., Pediatric Emergency Research Canada, Translating Emergency Knowledge for Kids [TREKK]), and other health provider groups (e.g., sports medicine physicians from the AMSafe clinic at the North East Community Health Center in Edmonton and the Acute Sport Concussion Clinic at the University of Calgary), both to obtain their input about the CP and to assist in its dissemination and implementation. We will also interview families who were referred to concussion clinics via the CP to solicit their feedback on what they found helpful and what would have worked better during their child's concussion experience.

In the dissemination phase, the study team and the site champions will share our findings through interactive education sessions with pediatric acute care providers at AHS sites. Additionally, we will make presentations at national professional and scientific conferences and publish peer-reviewed papers in clinical and scientific journals. The findings will be highlighted on the MNCY SCN website. In conjunction with the MNCY pediatric concussion workgroup, we will seek to spread and scale up the implementation of the CP to all pediatric acute care settings across the province.

30c We also plan to disseminate the project's findings more broadly, outside of Alberta. We are ideally situated to do so given our team's extensive links to important concussion and brain injury initiatives both nationally and internationally. Our team includes investigators who sit on the Federal working group for sport concussion guidelines, the Canadian Concussion Collaborative, the Canadian Traumatic Brain Injury Research Consortium, the Center for Disease Control Mild Traumatic Brain Injury Workgroup, the International Concussion in Sport Group, and the International Initiative in Traumatic Brain Injury Research (IntBIR). We will disseminate our findings to all of these groups, which include clinicians, researchers, sporting bodies, professional organizations, and research funding agencies.

Finally, we will develop a plan for data sharing, to insure the data from the project are available to other qualified investigators. This will likely take the form of a website that allows interested investigators to request data for specific planned analyses, subject to a University-approved data sharing agreement. The website will describe the parent project and provide a data dictionary that can be used to choose specific data elements to be included in requested datasets.

